### 10 CLINICAL EVALUATION PLAN AND STUDY VISITS

The time frames established by the Study Protocol should be observed for all the visits described below.

The study site personnel should make all efforts to conduct the assigned schedule of procedures and visits exactly as required by the Study Protocol.

All deviations from the study flow chart and procedures scheduled for the visits should be documented in the CRF.

#### 10.1 Pre-screening

A pre-screening visit is carried out for patients with gout who visit the physician-investigator as part of routine patient follow-up and do not experience an acute gout attack. At this visit, the

CONFIDENTIAL P. 48 of 84

patient is informed about the study procedures and the patient signs the Informed Consent to participate in the screening. The patient receives a copy of the Patient Information Sheet with Informed Consent Form for review and making a decision about participation in the study in the event of an acute gout attack.

# 10.2 Screening and treatment period

Screening procedures must be performed within 24 hours and the patient is randomized during this time. If necessary (in exceptional cases), the screening period can be extended, while randomization must be carried out no later than 120 hours (5 days) after the onset of an attack.

Patients randomized to the Voltaren® (diclofenac) group do not have to come to the study site on study days 10, 18 and 22, but they should complete the diary, if applicable, and the patient questionnaire on these days.

# Screening day (screening procedures and baseline assessments)

The patients are invited to participate in the study and are given a copy of the Patient Information Sheet with Informed Consent Form for review and making a decision about their participation. The patient's written informed consent to participation in the study must be obtained before any procedures scheduled in this study, including the screening procedures, are carried out.

Patients who have read the Patient Information Sheet and signed the Informed Consent Form will be assigned numbers by the online randomization system in the order in which they visit the study site during the screening visit procedures. The number for each patient will consist of two parts: the first two digits will indicate the site number, the next three digits will indicate the assigned serial number of the patient. The individual patient number is retained for subsequent randomization.

Example of patient number assignment: At site 1, the first patient who signs the informed consent form will be assigned number 01001, which will be retained through randomization. The second patient who signs the informed consent form is assigned number 01002. Let us assume that the second patient was not randomized. Then he drops out of the study with number 01002. The third patient receives number 01003. The number assigned to the patient will be indicated on all study documents and in the source documentation.

If a patient is withdrawn from the study during the screening period (an exclusion criterion identified, patient's refusal to participate, etc.), the reason for withdrawal should be specified in the screening log. In this case, the patient can take part in the study again.

After signing the informed consent form for participation in the clinical study, the following procedures are performed at screening:

• Confirmation of the diagnosis, documenting the information about the primary disease;

NOTE. The diagnosis of gout can be made at a visit to the study site during a current gout attack based on the American College of Rheumatology (ACR) and European League Against Rheumatism (EULAR) criteria of 2015 with the total score of 8. Uric acid level as the diagnostic criterion can be determined earlier, regardless of when. The highest uric acid levels ever measured must be used.

- Collection of demographic data, medical history, information about previous and concomitant therapy;
- Patient assessment using the TB risk assessment questionnaire;
- Measurement of height and weighing, calculation of body mass index (body mass index must be assessed before randomization);

CONFIDENTIAL P. 49 of 84

- Dispensing questionnaires to the patient to record the following:
  - o Pain intensity in the assessed joint according to VAS (screening score);
  - Health assessment questionnaire score (baseline value);
- Physician assessment of the degree of swelling, tenderness, erythema and movement restriction in the assessed joint (baseline value);
- Blood sampling for the following analyses:
  - O Diagnosis of infections: HIV, HBsAg and HCV Ab (rapid tests, the results must be evaluated before randomization);
  - o Diagnosis of infections: HIV, HBsAg, HCV Ab (central laboratory);
  - o Complete blood count with WBC differential (absolute neutrophil count, leukocyte and platelet counts must be assessed prior to patient randomization);
  - O Blood creatinine level (local laboratory, creatinine levels must be assessed prior to patient randomization);
  - O Diagnosis of tuberculosis: T-SPOT.TB test performed at screening or during the hospital stay (central laboratory);
  - Calculation of creatinine clearance (automatically in CRF using the Cockcroft-Gault formula);
  - o Blood chemistry with blood lipids (central laboratory);
  - Blood clotting tests (central laboratory);
  - Baseline sample for hs-CRP (central laboratory);
  - Baseline sample for serum amyloid protein A (central laboratory);
  - Baseline sample for cytokines (central laboratory);
  - O Serum pregnancy test for women of childbearing potential (the results must be assessed prior to patient randomization);
- Urinalysis;
- Physical examination (the results must be assessed prior to patient randomization);
- Vital signs (the results must be assessed prior to patient randomization);
- 12-lead ECG (the results must be assessed prior to patient randomization);
- Chest X-ray in 2 views (the results must be assessed prior to patient randomization);
- Serious adverse event recording;
- Eligibility assessment.

For patients meeting the eligibility criteria, the following procedures are performed immediately prior to randomization:

• Handing over to the patient a questionnaire for recording pain intensity in the assessed joint according to the VAS (baseline value recorded immediately (within 1 hour) before randomization).

CONFIDENTIAL P. 50 of 84

### Day 1 (randomization and initiation of therapy)

Patients meeting the eligibility criteria are randomized to receive therapy with either of the investigational products, RPH-104 or Voltaren® (diclofenac).

After randomization, the patients undergo the following procedures:

- Blood collection for the following tests (only for patients randomized to the RPH-104 group, prior to drug administration):
  - o Baseline blood sample to study the RPH-104 pharmacokinetics (central laboratory);
  - Baseline blood sample to study anti-RPH-104 antibody levels (central laboratory);
- Subcutaneous injection of RPH-104 (only for patients randomized to RPH-104 groups);

NOTE. The time of administration of RPH-104 is recorded in the source documentation and CRF. Sampling time for subsequent blood samples to assess pharmacokinetics, pain intensity in the assessed joint, and patient global assessment of efficacy are counted from this time. The acceptable time intervals for these procedures are indicated in the Study Procedure Table (see Section 3).

Evaluation of pain intensity in the assessed joint and patient global assessment of efficacy are performed before pharmacokinetic blood sampling in accordance with the pre-specified time intervals for these procedures.

• Dispensing Voltaren® (diclofenac) and Ortanol® (omeprazole) to the patient in an amount sufficient for use until the end of the treatment period (only for patients randomized to the Voltaren® (diclofenac) group);

*NOTE.* Subcutaneous injection of RPH-104 or the first dose of Voltaren® (diclofenac) must be given within 30 minutes after randomization.

By the decision of the investigator, after the use of the investigational products, patients can be hospitalized and remain under observation in the hospital or continue to participate in the study on an outpatient basis.

After administration of the investigational products, outpatients remain under the supervision of the investigator for at least 3 hours, after which they are allowed to leave the study site. These patients should return to the study site for all analyses and assessments in accordance with the study procedure schedule (Table 3.1).

- Dispensing questionnaires to the patient to record the following:
  - Pain intensity in the assessed joint according to VAS (at 15, 30, 45 minutes, 1, 1.5 h after the use of the investigational product);
  - O Patient global assessment of the efficacy using a categorical scale (at 15, 30, 45 minutes, 1, 1.5 h);
- Evaluation of RPH-104 injection site reactions 15 minutes after injection (only for patients who received RPH-104);
- Collecting information on concomitant therapy and adverse events;
- Handing over the Patient Diary.

CONFIDENTIAL P. 51 of 84

# **Day 1 (2 and 8 hours after the start of therapy)** – only for patients randomized to RPH-104 groups

- Dispensing questionnaires to the patient to record the following:
  - o Pain intensity in the assessed joint according to VAS;
  - o Patient global assessment of the efficacy using a categorical scale.
- Blood sampling for the following analyses:
  - Assessment of RPH-104 pharmacokinetics (central laboratory);
- Evaluation of RPH-104 injection site reactions;
- Collection of information on concomitant therapy and adverse events.

# Day 1 (4 hours after the start of therapy) – only for patients randomized to RPH-104 groups

- Dispensing questionnaires to the patient to record the following:
  - o Pain intensity in the assessed joint according to VAS;
  - o Patient global assessment of the efficacy using a categorical scale;
- Evaluation of RPH-104 injection site reactions;
- Collection of information on concomitant therapy and adverse events.

# Day 2 (24 hours after the start of therapy)

- Assessment of vital signs;
- Dispensing questionnaires to the patient to record the following:
  - o Pain intensity in the assessed joint according to VAS;
  - Patient global assessment of the efficacy using a categorical scale.
- Blood sampling for the following analyses:
  - Assessment of RPH-104 pharmacokinetics (only for patients randomized to the RPH-104 groups, central laboratory);
  - o hs-CRP (central laboratory);
  - o Serum amyloid protein A (central laboratory);
  - Cytokines (central laboratory);
- Assessment of the degree of swelling, tenderness, erythema and movement restriction in the assessed joint;
- Evaluation of RPH-104 injection site reactions (only for patients who received RPH-104);
- Collection of information on concomitant therapy and adverse events;
- Patient diary collection and registration of entered data;
- Handing over the Patient Diary.

CONFIDENTIAL P. 52 of 84

## Day 3 (48 hours after the start of therapy)

- Dispensing questionnaires to the patient to record the following:
  - o Pain intensity in the assessed joint according to VAS;
  - o Patient global assessment of the efficacy using a categorical scale.
- Blood sampling for the following analyses:
  - Assessment of RPH-104 pharmacokinetics (only for patients randomized to the RPH-104 groups, central laboratory);
- Assessment of the degree of swelling, tenderness, erythema and movement restriction in the assessed joint;
- Evaluation of RPH-104 injection site reactions (only for patients who received RPH-104);
- Collecting information on concomitant therapy and adverse events;
- Patient diary collection and registration of entered data;
- Handing over the Patient Diary.

#### Day 4 (72 hours after the start of therapy)

- Assessment of vital signs;
- Dispensing questionnaires to the patient to record the following:
  - o Pain intensity in the assessed joint according to VAS;
  - o Patient global assessment of the efficacy using a categorical scale.
- Blood sampling for the following analyses:
  - Assessment of RPH-104 pharmacokinetics (only for patients randomized to the RPH-104 groups, central laboratory);
  - hs-CRP (central laboratory);
  - Serum amyloid protein A (central laboratory);
  - Cytokines (central laboratory);
- Assessment of the degree of swelling, tenderness, erythema and movement restriction in the assessed joint;
- Evaluation of RPH-104 injection site reactions (only for patients who received RPH-104);
- Collecting information on concomitant therapy and adverse events;
- Patient diary collection and registration of entered data;
- Handing over the Patient Diary.

# Day 5 (96 hours after the start of therapy)

- 12-lead ECG;
- Urinalysis;

CONFIDENTIAL P. 53 of 84

- Assessment of vital signs;
- Weighing;
- Dispensing questionnaires to the patient to record the following:
  - o Pain intensity in the assessed joint according to VAS;
  - o Patient global assessment of the efficacy using a categorical scale.
- Blood sampling for the following analyses:
  - Assessment of RPH-104 pharmacokinetics (only for patients randomized to the RPH-104 groups, central laboratory);
  - o Complete blood count (local laboratory);
  - o Blood creatinine level (local laboratory);
  - Calculation of creatinine clearance (automatically in CRF using the Cockcroft-Gault formula);
  - Blood chemistry with blood lipids (central laboratory);
  - o Blood clotting tests (central laboratory);
  - o hs-CRP (central laboratory);
  - o Serum amyloid protein A (central laboratory);
  - Cytokines (central laboratory).
- Assessment of the degree of swelling, tenderness, erythema and movement restriction in the assessed joint;
- Evaluation of RPH-104 injection site reactions (only for patients who received RPH-104);
- Collecting information on concomitant therapy and adverse events;
- Patient diary collection and registration of entered data;
- Handing over the Patient Diary.

### Day 6 (120 hours after the start of therapy)

- Assessment of vital signs;
- Dispensing questionnaires to the patient to record the following:
  - o Pain intensity in the assessed joint according to VAS;
  - o Patient global assessment of the efficacy using a categorical scale.
- Blood sampling for the following analyses:
  - Assessment of RPH-104 pharmacokinetics (only for patients randomized to the RPH-104 groups, central laboratory);
  - hs-CRP (central laboratory);
  - o Serum amyloid protein A (central laboratory);
  - Cytokines (central laboratory);

CONFIDENTIAL P. 54 of 84

- Assessment of the degree of swelling, tenderness, erythema and movement restriction in the assessed joint;
- Evaluation of RPH-104 injection site reactions (only for patients who received RPH-104);
- Collecting information on concomitant therapy and adverse events;
- Patient diary collection and registration of entered data;
- Handing over the Patient Diary.

## Day 10 (216 hours after the start of therapy) and Day 18 (408 hours after the start of therapy)

- Blood sampling for the following analyses:
  - Assessment of RPH-104 pharmacokinetics (only for patients randomized to the RPH-104 groups, central laboratory);
- Dispensing questionnaires to the patient to record the following:
  - o Pain intensity in the assessed joint according to VAS;
  - o Patient global assessment of the efficacy using a categorical scale.
- Assessment of the degree of swelling, tenderness, erythema and movement restriction in the assessed joint;
- Evaluation of RPH-104 injection site reactions (only for patients who received RPH-104);
- Collecting information on concomitant therapy and adverse events;
- Patient diary collection and registration of entered data;
- Handing over the Patient Diary.

## Day 15 (336 hours after the start of therapy)

- Urinalysis;
- Dispensing questionnaires to the patient to record the following:
  - o Pain intensity in the assessed joint according to VAS;
  - o Patient global assessment of the efficacy using a categorical scale.
  - Health assessment questionnaire completion;
- Blood sampling for the following analyses:
  - Assessment of RPH-104 pharmacokinetics (only for patients randomized to the RPH-104 groups, central laboratory);
  - o A study of anti-RPH-104 antibodies (only for patients randomized to the RPH-104 groups, central laboratory);
  - Complete blood count (local laboratory);
  - o Blood creatinine level (local laboratory);
  - Calculation of creatinine clearance (automatically in CRF using the Cockcroft-Gault formula);

CONFIDENTIAL P. 55 of 84

- o Blood chemistry with blood lipids (central laboratory);
- Blood clotting tests (central laboratory);
- hs-CRP (central laboratory);
- Serum amyloid protein A (central laboratory);
- Cytokines (central laboratory);
- Assessment of the degree of swelling, tenderness, erythema and movement restriction in the assessed joint;
- Assessment of vital signs;
- Weighing;
- Physical examination;
- Evaluation of RPH-104 injection site reactions (only for patients who received RPH-104);
- Collecting information on concomitant therapy and adverse events;
- Patient diary collection and registration of entered data;
- Handing over the Patient Diary.

#### Day 22 (504 hours after the start of therapy)

- Assessment of vital signs;
- Dispensing questionnaires to the patient to record the following:
  - o Pain intensity in the assessed joint according to VAS;
  - o Patient global assessment of the efficacy using a categorical scale.
- Blood sampling for the following analyses:
  - Assessment of RPH-104 pharmacokinetics (only for patients randomized to the RPH-104 groups, central laboratory);
- Assessment of the degree of swelling, tenderness, erythema and movement restriction in the assessed joint;
- Evaluation of RPH-104 injection site reactions (only for patients who received RPH-104):
- Collecting information on concomitant therapy and adverse events;
- Patient diary collection and registration of entered data;
- Handing over the Patient Diary.

## Day 29 (672 hours after the start of therapy)

- Dispensing questionnaires to the patient to record the following:
  - o Pain intensity in the assessed joint according to VAS;
  - o Patient global assessment of the efficacy using a categorical scale;

Health assessment questionnaire completion;

CONFIDENTIAL P. 56 of 84

- Blood sampling for the following analyses:
  - Assessment of RPH-104 pharmacokinetics (only for patients randomized to the RPH-104 groups, central laboratory);
  - hs-CRP (central laboratory);
  - Serum amyloid protein A (central laboratory);
  - o Cytokines (central laboratory);
- Assessment of the degree of swelling, tenderness, erythema and movement restriction in the assessed joint;
- Assessment of vital signs;
- Evaluation of RPH-104 injection site reactions (only for patients who received RPH-104);
- Collecting information on concomitant therapy and adverse events;
- Patient diary collection and registration of entered data;
- Handing over the Patient Diary.

#### Day 45 (1056 hours after the start of therapy)

- 12-lead ECG;
- Urinalysis;
- Dispensing questionnaires to the patient to record the following:
  - o Pain intensity in the assessed joint according to VAS;
  - o Patient global assessment of the efficacy using a categorical scale;
  - o Health assessment questionnaire completion.
  - o Blood sampling for the following analyses:
  - O Assessment of RPH-104 pharmacokinetics (only for patients randomized to the RPH-104 groups, central laboratory);
  - A study of anti-RPH-104 antibodies (only for patients randomized to the RPH-104 groups, central laboratory);
  - Complete blood count (local laboratory);
  - o Blood creatinine level (local laboratory);
  - Calculation of creatinine clearance (automatically in CRF using the Cockcroft-Gault formula);
  - Blood chemistry with blood lipids (central laboratory);
  - Blood clotting tests (central laboratory);
  - hs-CRP (central laboratory);
  - Serum amyloid protein A (central laboratory);
  - Cytokines (central laboratory);
  - o Serum pregnancy test for women of childbearing potential;

CONFIDENTIAL P. 57 of 84

- Assessment of the degree of swelling, tenderness, erythema and movement restriction in the assessed joint;
- Assessment of vital signs;
- Weighing;
- Physical examination;
- Evaluation of RPH-104 injection site reactions (only for patients who received RPH-104);
- Collecting information on concomitant therapy and adverse events;
- Patient diary collection and registration of entered data.

# Day 60 ( $\pm$ 7 days)

On this day, the Investigator contacted the patient over the phone to collect information about adverse events, their characteristics (onset time, resolution time, severity, relationship to the investigational product, etc. as described in Section 12 of this protocol).

# 10.3 Follow-up visit for early patient withdrawal from the study

The follow-up visit for patients who withdraw from the study early is carried out for 7 days after the decision on early withdrawal. The minimum list of examinations at the Follow-up Visit is as follows:

- Adverse event recording
- Collection of information on concomitant therapy
- Assessment of vital functions
- Complete physical examination
- Weighing
- 12-lead ECG
- Urinalysis
- Blood sampling for the following analyses:
  - o Complete blood count;
  - O Blood chemistry with blood lipids (central laboratory); creatinine (local site laboratory);
  - Calculation of creatinine clearance (automatically in CRF using the Cockcroft-Gault formula);
  - Blood clotting tests (central laboratory);
  - o Serum pregnancy test for women of childbearing potential;
- Blood samples to assess the pharmacokinetics of the investigational product and antidrug antibodies (only for patients who received RPH-104, central laboratory).

CONFIDENTIAL P. 58 of 84

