### 4.3.2 Clinical pharmacology trials

Pharmacokinetics of RPH-104 in humans

At the time of writing this protocol, data on the pharmacokinetics of RPH-104 were available for a single subcutaneous injection in healthy volunteers at doses of 4 and 20 mg. The results of evaluation of pharmacokinetic RPH-104 parameters from phase 1 studies in healthy volunteers are provided in Table 4.1 below.

Table 4.1 Pharmacokinetic parameters of RPH-104 after a single subcutaneous injection in healthy volunteers

PK parameters/RP H-104 dose	4 mg (N=5)	20 mg (N=5)	40 mg (N=3)	80 mg (N=5)	160 mg (N=5)
C max (ng/mL)	$198 \pm 89.1$	$1280 \pm 402$	$1650 \pm 257$	5120 ± 1410	$10300 \pm 4470$
AUC(0-t) (h*ng/mL)	74500 ± 247 00	430000 ± 9570 0	661000 ± 1580 00	1610000 ± 3170 00	3390000 ± 14500 00
AUC(0-∞) (h*ng/mL)	87100 ± 283 00	505000 ± 1050 00	804000 ± 1960 00	1850000 ± 3530 00	3990000 ± 18100 00
t 1/2 (h)	$245 \pm 9.50$	$249 \pm 6.08$	$255 \pm 43.1$	$235\pm22.8$	$243 \pm 40.4$
tmax (h)	96 (94.4 – 192)	96 (48. – 96.2)	120 (96 – 192)	96 (72 – 120)	120 (72 – 120)

Note: data are presented as means  $\pm$  standard deviation, except for tmax values, where the median is presented (minimum value – maximum value)

As can be seen from the presented table, the maximum concentration of RPH-104 appears in the blood on average approximately 4-5 days after the subcutaneous administration of RPH-104. The

CONFIDENTIAL P. 28 of 84

study results showed that RPH-104 at doses ranging from 4 to 160 mg has linear pharmacokinetics and its half-life is approximately equal to 10 days.

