Information about the investigational product used for the treatment of acute gout in the patients in this study (RPH-104 or Voltaren® (diclofenac)) and the dose of RPH-104 is unblinded to the patients and physicians. Patients who do not tolerate pain receive the rescue medication after 2 hours and until Day 45 of the study after the first use of rescue medication to intensify therapy. The rescue medication is triamcinolone 40 mg intramuscularly. If an attack recurred after the use of the rescue medication, treatment of acute gout attack is carried out in accordance with the standard practice of the hospital.

[figure not shown]
The primary efficacy variable is assessed 72 hours after initiation of the investigational product use. Secondary efficacy variables are evaluated over a 45 day period of therapy and follow-up.

[figure not shown]
The safety of the investigational product is assessed over a 60-day period of therapy and follow-up.

The study flow diagram is shown in Figure 6.1. The total duration of the study for one patient does not exceed 70 days.

RPH-104 4 mg once: n=15

CONFIDENTIAL P. 36 of 84

\* Screening procedures must be performed within 24 hours and the patient is randomized during this time. If necessary (in exceptional cases), the screening period can be extended, while randomization must be carried out no later than 120 hours (5 days) after the onset of an attack.

Figure 6.1 Flow diagram of the study design.

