# 8 WITHDRAWAL FROM THE STUDY AND PREMATURE TERMINATION OF THE STUDY

If a decision has been made to withdraw a patient early from the study following the study drug administration, the investigator must schedule a follow-up visit for the patient within 7 days, if possible. If this is not possible, the patient must be invited for a follow-up visit as soon as possible in the period exceeding 7 days. At this visit, it is necessary to carry out all the assessments specified for this visit (see Section 10.3).

CONFIDENTIAL P. 40 of 84

If a patient is excluded from the study due to an AE or a laboratory abnormality, the patient must be monitored until the AE resolved or his/her condition stabilized.

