# 8.1 Early withdrawal from the study

The withdrawal criteria are:

- Withdrawal of informed consent.
- Patient's death.
- Patient's pregnancy.
- A significant protocol deviation, which, in the opinion of the Investigator, and upon agreement with the Sponsor, could result in an incorrect interpretation of the study results.

The use of a rescue medication, prohibited drugs, and missing certain procedures or individual visits are generally not the reasons for discontinuation of the patient from the study. In these cases, the patient should be offered to continue the visits and examinations in accordance with the clinical study protocol.

The Investigator should make all reasonable efforts to determine the reason of the patient's withdrawal from the study. The date and reason for the patient's early withdrawal from the study had to be clearly described in the CRF for any patient who received at least one dose of the investigational product.

If a patient is withdrawn from the study due to pregnancy, the Investigator provides the Sponsor with information concerning the pregnancy outcome (see Section 12.7).

Regardless of the reasons for early withdrawal from the study, no replacement of withdrawn patients is to be made.

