# 8.2 Premature termination of the study at an individual study site and premature termination of the study in general

The sponsor reserves the right to terminate the study at an individual study site or at all sites at any time due to reasons of medical and/or administrative nature.

In case of premature study termination, the Investigator should, regardless of the reason for this decision, immediately notify all patients and ensure their follow-up and further treatment. The sponsoring company will notify in writing the Investigator and regulatory authorities about the termination of the study, indicating the reasons for this decision.

In case of premature termination of the study, the Investigator should, if possible, conduct the procedures and evaluations scheduled for the follow-up visit for early withdrawal in all patients who have not completed their participation in the study by this time (see Section 10.3).

CONFIDENTIAL P. 41 of 84

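### No scheduled safety contact follows the early-withdrawal visit, so new adverse events after it are not actively collected, although safety is assessed over 60 days and treatment-emergent events are counted to Day 45

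*Combined protocol and SAP*

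**What the plan says.** Section 8 says that after a decision to withdraw a dosed patient "the investigator must schedule a follow-up visit for the patient within 7 days, if possible"; failing that, "the patient must be invited for a follow-up visit as soon as possible in the period exceeding 7 days". Section 10.3 repeats the 7-day timing ("The follow-up visit for patients who withdraw from the study early is carried out for 7 days after the decision on early withdrawal") and gives a minimum list of examinations: AEs, concomitant therapy, vital signs, physical examination, weight, ECG, laboratory tests and, for RPH-104 patients, pharmacokinetic and antibody samples. The visit is timed from the decision, not from the injection.

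Section 8.2 asks the investigator, if the study is stopped early, to "conduct the procedures and evaluations scheduled for the follow-up visit for early withdrawal in all patients who have not completed their participation" where possible, and to ensure patients' follow-up and further treatment.

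The Day 60 telephone call for AEs is described in Section 10.2. Table 3.1 shows D60 and FUV (the early-withdrawal visit) as separate columns, and no footnote links them.

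Section 6.2 states that "The safety of the investigational product is assessed over a 60-day period of therapy and follow-up". Section 13.6.1 counts AEs as treatment-emergent up to 45 days after administration. Section 13.1.1 puts everyone who received at least one dose in the safety population. Section 4.3.2 reports that RPH-104 "has linear pharmacokinetics and its half-life is approximately equal to 10 days".

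**The concern.** RPH-104 is a single injection, so leaving the study does not end exposure. A patient who withdraws soon after dosing can have the last scheduled safety contact while the concentration is still near its maximum. That patient then stays in the denominator of the AE rates for the dose group. An AE that begins later is recorded only if someone happens to report it.

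In arms of 14 or 15 patients, a few such cases could make a dose look better tolerated than it was. Section 13.6.1 asks for no count of patients with shortened observation, so a reader of the report could not see this.

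Not every early departure is a refusal of contact. Section 8.1 also lists "A significant protocol deviation, which, in the opinion of the Investigator, and upon agreement with the Sponsor, could result in an incorrect interpretation" of results as a reason for withdrawal, and a sponsor's decision to terminate is another. Many of these patients could be telephoned.

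**Working it through.** **1. Inputs (Table 4.1, 23 healthy volunteers, 3 to 5 per dose).** Mean half-lives at 4, 20, 40, 80 and 160 mg are 245, 249, 255, 235 and 243 h. Median tmax values are 96, 96, 120, 96 and 120 h.

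**2. The plan's own figures.** Dividing by 24 gives half-lives of 10.2, 10.4, 10.6, 9.8 and 10.1 days, and tmax of 4 to 5 days. Both statements in Section 4.3.2 reproduce.

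**3. Model (an assumption, not in the plan).** One compartment with first-order absorption:
- ke = ln 2 / t½
- ka solved from tmax = ln(ka/ke)/(ka − ke)
- share of AUC(0-∞) still to come at time t = [ka·exp(−ke·t) − ke·exp(−ka·t)]/(ka − ke)
- concentration at t relative to Cmax = [exp(−ke·t) − exp(−ka·t)] / [exp(−ke·tmax) − exp(−ka·tmax)]

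**4. Early case.** Table 3.1 sets Day 2 at 24 h. Withdrawal on Day 2 with the visit 7 days later puts the visit at 24 + 168 = 192 h, which is Day 9. For 4 mg, ke = 0.00283 and ka = 0.02589 per hour, and the share remaining is (0.02589 × 0.5809 − 0.00283 × 0.0069)/0.02306 = 0.65. All doses:

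| Dose (mg) | AUC still to come at 192 h | Concentration relative to Cmax |
|---|---|---|
| 4 | 65% | 85% |
| 20 | 66% | 85% |
| 40 | 69% | 92% |
| 80 | 64% | 84% |
| 160 | 68% | 92% |

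192 h is 8 days after dosing, so 45 − 8 = 37 of the 45 treatment-emergent days fall after the last scheduled contact.

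**5. Dependence on the timing of the visit.**

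| Last visit, days after dosing | AUC still to come |
|---|---|
| 7 | 69-73% |
| 8 | 64-69% |
| 14 | 42-47% |
| 21 | 26-30% |
| 44 (Day 45 visit) | 5-7% |
| 59-60 (Day 60 call) | about 2% |

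Half of the exposure is reached 11.5 to 13.0 days after injection. With the visit 7 days after the decision, more than half remains only for withdrawal within about 4.5 to 6 days of dosing (11.5 − 7 to 13.0 − 7). With the visit on the day of the decision, that extends to about day 12.

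**6. Model check.** AUC(0-t)/AUC(0-∞) in Table 4.1 is 0.82-0.87, so 13-18% was extrapolated. The model leaves about 14-19% at days 28 to 30. The two agree if phase 1 sampling ended near day 30, which is assumed from the visit description in Section 4.3.3.

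**7. Weight of one patient.** 1/14 = 7.1% in the 20 to 160 mg arms and the diclofenac arm; 1/15 = 6.7% in the 4 mg arm.

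**The case against.** The strongest reply is that much safety information is still collected after withdrawal. After exclusion for an AE or laboratory abnormality, "the patient must be monitored until the AE resolved or his/her condition stabilized". Section 12.9 follows all AEs to resolution or stabilisation. Section 12.5 requires reporting of serious AEs up to the end of the study, and of related ones even afterwards. Sections 8.1 and 12.7 follow pregnancies to their outcome. All of this stands. A reader might infer that events in withdrawn patients are simply never collected, and the documents do not support that. These provisions do, however, either follow events already known or rely on an event coming to the site's notice. None of them asks the patient about new AEs.

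Other points that stand:
- **Silence, not exclusion.** No section bars withdrawn patients from the Day 60 call, and the Section 10.3 list is a minimum. But a minimum list of examinations creates no later contact, and sites could read the silence differently.
- **Early withdrawal is the worst case.** A visit 21 days after dosing leaves 26-30% of exposure. Section 8 also allows the visit to fall later than 7 days after the decision, which narrows the gap.
- **Numbers may be small.** Treatment is a single dose, and Section 8.1 says that rescue use, prohibited drugs and missed visits are generally not reasons to discontinue.
- **Termination.** A reader might link the gap to the planned interim analysis. Section 13.7 says that all 47 patients in it have completed participation, so only patients enrolled later could be ongoing at a termination.
- **Both treatments are affected.** The same visit applies to diclofenac patients. Only the argument from continuing exposure is particular to RPH-104.

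**Conclusion.** The point holds as a limited gap in safety ascertainment. Followed as written, the plan schedules no active enquiry about new AEs after the early-withdrawal visit, while withdrawn patients still count in the safety denominators for a 60-day assessment and a 45-day treatment-emergent window.

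The size depends on when the visit falls. With a last visit at 192 h, 64-69% of exposure and 37 of 45 treatment-emergent days follow it. More than half of the exposure follows it only if it takes place before about day 12.

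A reader might go further and conclude that the AE rates are understated. The documents do not show that: they give no withdrawal rate, and with no withdrawals nothing is lost. The rates may be understated if patients withdraw.

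The exposure shares rest on a one-compartment approximation and on healthy-volunteer data; patients with gout may differ. The absence of a later scheduled contact does not depend on the model.

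**What to change.** In Sections 8, 8.2 and 10.3, and in a footnote to the FUV column of Table 3.1, state that any dosed patient who leaves early, or is ongoing when the study is terminated, also receives the existing Day 60 telephone contact, timed from dosing, unless the patient refuses further contact.

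In Section 13.6.1, report for each arm the number of patients without safety information through Day 45 and through Day 60.

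With the call in place, the modelled exposure after the last contact falls to about 2%, as for completers. The cost is protocol wording, one telephone call per patient who leaves early, and one line in the safety tables. The limits are that AEs would be collected partly by recall, and that the call would reach few of those who withdraw consent and decline contact.
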